Further patient data that will be analyzed as secondary outcome measures at 2 and 6 weeks are adherence to allocated treatment and adverse events related to IPC. Adverse events (binary) that will be registered are 1) Any damage to the skin of the legs including infection. 2) Any reasons for prematurely stopping the IPC. 3) Any fall associated with significant injury occurring within 6 weeks of enrollment. The frequency of the adverse events of each group will be presented⁹.

Health economic analyses, together with Karolinska Institutet, LIME, Med. dr. [name], of the trial treatment effects will involve a within-trial evaluation of cost effectiveness integrated into a decision-analytic model of longer run costs and health effects.

Study Design (PICO)

“STOP leg clots” is an international, multicentre prospective randomized, controlled, parallel group trial with blinded assessment of the outcome. The allocation ratio is 1:1. The study has an Ethical review board approval 2016/1753-31 and is registered at clinicaltrials.gov.

Patients: At least 20 hospitals in a minimum of twelve regions have accepted to participate, and this captures a study population, which is representative of Sweden. The included patients, ATR and ankle fractures, are representative of, and constitute a large part of the population with lower limb immobilization. Moreover, patients with ATR and AF have

demonstrated low- or non-effectiveness of LMHW prophylaxis also in relation to the risk of bleeding complications^{3 4}. Therefore, there is a need for an alternative prophylaxis with documented effects.

In the perspective that different hospitals have different clinical traditions/indications for surgery of ATR and AF we have chosen to include both operated and non-operated ATR/AF, since both groups are equally served by VTE prophylaxis. Earlier studies have shown a just as high incidence of VTE in non-operated as in operated ATR/AF⁶, further indicating a benefit of demonstrating a VTE risk reduction in both operated/non-operated lower limb immobilized patients. Surgery vs. no surgery will be accounted for in the statistical analysis.

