Intervention: There is a need for new VTE prophylactic methods, especially in lower limb immobilized patients. IPC has been demonstrated cost effective both as adjuvant and versus no pharmacoprophylaxis in hospitalized patients by NICE. However, in an outpatient setting there are yet only recent short-term data of the efficacy of IPC. There is a need for data on the efficacy of IPC during long-term leg immobilization to inform guidelines.

The intervention, *addition of IPC to routine care*, will be administered in the emergency department or in the outpatient clinic. Patients will during the six weeks of lower limb immobilization receive bilateral calf IPC (Venaflo Elite, DJO LLC, Vista, CA, USA) applied under an orthosis (Aircast® AirSelect Elite, DJO LLC, Vista, CA, USA). This IPC-system delivers rapid inflation and graduated sequential compression. The IPC device is mobile and should therefore not restrict patient mobilization, but can be taken off if the patient wants to mobilize independently. The patients will be instructed to apply the IPC-therapy continuously, both day and night. Compliance with the treatment will be registered by both the patient and by the device⁹. American College of Chest Physicians recommend that efforts should be made to achieve 18 h of daily compliance with IPC in hospitalized patients¹⁷. However, there are no recommendations for mobile outpatients. Outpatients were in our recent study recommended at least 6h daily therapy, and in this study we will increase the recommendation to 10h/daily. Graduated compression stockings are part of IPC-care and these should be applied and worn under the IPC sleeves on both legs. IPC will be discontinued if the patient declines to continue IPC or had adverse effects of the IPC that warrants removal. At the 2 and 6 weeks visit the orthosis will be removed by a nurse and the patient will be examined by an orthopaedic surgeon (masked to the treatment allocation), who will document compliance and adverse events. At the 6 weeks visit the patient will also be sent for CDU-examination, which will document the main outcome. Patients will during the six weeks leg immobilization be weight-bearing with crutches or non-weight-bearing with crutches according to the preference of the orthopedic surgeon (masked to the treatment allocation). Weight-bearing will be recorded and accounted for in the statistical analysis.

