Comparator: Since there are no documented highly effective therapies for DVT reduction during leg immobilization, and guidelines vary regarding prophylaxis, we chose to use treatment-as-usual as a comparator, regardless of LMHW use or not^{3 4}. Based on our calculations less 10% of the patients will receive LMHW in clinical practice and our power calculations has taken this into account. NICE has stated that LMWH is not a feasible general treatment, especially health economically, during six weeks for all patients with leg immobilization. One review, including 1,490 patients from six randomized trials, showed a small reduction in DVTs using LMHW⁸. However, they concluded that more research is needed to develop more effective and safe thromboprophylactic treatments. Moreover, since a study with LMHW as a comparator would necessitate too many patients - this was not an option. The main research question remains: Is adjuvant IPC more effective than routine care for reducing the incidence of VTE in patients during lower limb immobilization? The usage of no general VTE-prevention in the comparator group is moreover justified since a DVT-screening will be performed on all patients. LMWH vs. no LMWH will be accounted for in the statistical analysis. If a VTE is detected we will follow clinical guidelines and initiate

pharmacological VTE-treatment.

The comparator, **routine care**, lower limb immobilization will be administered by normal routine in the emergency department or in the outpatient clinic. Routine care include that the lower limb will be immobilized in an orthosis or a below-knee plaster cast according to local routines. At the 2 and 6 weeks visit the orthosis/plaster cast will be removed by a nurse who will document compliance. Subsequently, the patient will be examined by an orthopaedic surgeon (masked to the treatment allocation), who will document adverse events. At the 6-8 weeks visit the patient will also be sent for CDU-examination, which will document the main outcome. Patients will during the six weeks leg immobilization be weight-bearing with crutches or non-weight-bearing with crutches according to the preference of the orthopedic surgeon (blinded to the treatment group). Weight-bearing will be recorded and accounted for in the statistical analysis.

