National collaborators from 12 regions in Sweden, 23 hospitals, have already agreed to participate in this multicenter study. Stockholm region: Karolinska University Hospital Solna and Huddinge, Danderyd Hospital, Stockholm South General Hospital, Södertälje and Norrtälje Hospital. Uppsala region: Uppsala University Hospital. Östergötland region: Linköping University Hospital. Gotland region: Visby lasarett. Skåne region: Skåne University Hospital in Lund and in Malmö. Halland region: Kungsbacka Hospital. Västra Götalands region: Sahlgrenska University Hospital, Östra Hospital, Kungälv Hospital. Värmland region:

Karlstad Central Hospital. Gävleborg Region: Gävle and Bollnäs Hospital. Västerbotten region: University Hospital Umeå. Örebro: University Hospital Örebro, Karlskoga lasarett, Lindesberg lasarett. Jönköping region: Eksjö Hospital.

International collaborators from Rizzoli hospital in Bologna, Italy have shown interest to participate.

Estimated sample size and power

We plan to include at least 1400 patients, with 10% drop-out accounted for, although our earlier study demonstrated a 5.3% drop-out⁹. Many patients will in clinical routine receive LMWH, which is accounted for. This gives the trial 90% power (alpha 0.05) to identify an absolute risk reduction of 8% (28% vs. 20%) and relative risk reduction of 29% in primary outcome. The expected relative risk reduction is higher, 40%, and the minimum clinical relevant absolute risk reduction in primary outcome between the groups is 4% based on recent studies^{9,26}.

The frequency of our primary outcome is given from recent studies showing a 50% rate of CDU-verified DVTs after ATR and 25% rate after ankle fracture (AF)^{9,27}. This gives a total DVT-rate of 33% when including two AF for every ATR. As extra precautions we reduced the expected total DVT-rate from 33% to 28% and reduced the relative risk reduction from 40% to 30%.

The 1400 included patients will consist of at least 400 ATR- and at least 1000 AF-patients, with the same drop out as above. For subgroup analyses (ATR / AF) this gives the trial 80% power (alpha 0.05) to detect a 30% relative risk reduction and an absolute risk reduction of 8% (25% vs. 17%) for AF and 15% (50% vs. 35%) for ATR in primary outcome.

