The randomisation form should be filed in the patient's medical notes, along with one copy of the signed informed consent form and patient brochure. The patient should receive a patient brochure along with a signed copy of the consent form. Copies should also be kept in the site file. The treatment allocation will be blinded for the assessors of outcome; i.e. ultrasonographers doing the CDU, physiotherapists or nurses performing the patient reported outcomes. The IPC-therapy will, due to its nature, not be blinded to the patient and the clinician applying the therapy.

Statistical analysis plan ([name], statistician)

All analyses will be based on intention to treat. We will analyze patients in the groups they are randomized to, regardless of treatment received. A patient might be withdrawn because of severe non-adherence or withdrawal of consent by the patient. For binary outcomes (e.g. occurrence of a primary or secondary outcome OR not), outcomes will be presented as odds ratios and 95% confidence intervals, adjusted using logistic regression for the factors used in the minimization algorithm and weight-bearing. We will calculate absolute reductions in risk from these values, as presented in the reference with similar study design²⁶.

Group differences for ordinal secondary outcome data, such as the patient-reported data (ATRS and OMAS), will be analyzed by nonparametric tests²⁰. Group differences for EQ5D-5L (index scale), FAOS (ratio scale) and continuous secondary outcome data will be analyzed by t-tests if the data are normally distributed, and using an appropriate nonparametric test otherwise.

Subgroup analyses will be performed to determine whether certain types of patients might gain greater or less benefit from IPC. We will estimate the effect of treatment allocation on the primary outcome subdivided by key baseline variables and adjusted for the other factors included in the minimization algorithm. Subgroup analyses will be performed by observing the change in log-likelihood when the interaction between the treatment and the subgroup is added into a logistic regression model. We will determine whether there is significant heterogeneity between these subgroups. The following preplanned subgroup analyses will be performed:

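### The plan converts adjusted odds ratios to absolute risk reductions by a method given only by citation; standardising from the same model would avoid possible under-coverage and a small exaggeration of the effect

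*Combined protocol and SAP*

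**What the plan says.** Under Statistical analysis plan, binary outcomes are presented as odds ratios with 95% confidence intervals, "adjusted using logistic regression for the factors used in the minimization algorithm and weight-bearing". The next sentence reads: "We will calculate absolute reductions in risk from these values, as presented in the reference with similar study design". The values meant are the adjusted odds ratios and their intervals. The reference is number 26, a trial of IPC in stroke patients.

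Weight-bearing is the only covariate named there, and the minimization factors are not listed anywhere. Study Design (PICO) makes three related promises:
- Patients paragraph: "Surgery vs. no surgery will be accounted for in the statistical analysis".
- Intervention and Comparator paragraphs: "Weight-bearing will be recorded and accounted for in the statistical analysis".
- Comparator paragraph: "LMWH vs. no LMWH will be accounted for in the statistical analysis".

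Injury type and age (40 or over) appear in the preplanned subgroup analyses. That they are also adjustment factors is an inference.

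Estimated sample size and power states both the design effect (28% vs 20%, 8 points) and the minimum clinically relevant effect (4 points) as absolute reductions.

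**The concern.** An odds ratio does not fix a risk difference. A control risk is needed, and the plan does not say which. The simplest reading is that the adjusted odds ratio and its two limits are applied to the observed overall control risk. Two things then go wrong.

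1. The interval carries the uncertainty of the odds ratio but treats the control risk as known.
2. An odds ratio adjusted for prognostic covariates lies further from 1 than the marginal odds ratio, even with perfect balance (non-collapsibility). Pairing it with a marginal control risk therefore exaggerates the absolute effect. This does not shrink with sample size.

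Readers will set the reported reduction and its interval beside the plan's 8 and 4 points, so this is the scale on which the result will be judged clinically.

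**Working it through.** **Inputs.** From Estimated sample size and power: risks 28% and 20%; 1400 patients less 10% drop-out = 1260, or 630 per arm at 1:1; DVT 50% after ATR and 25% after AF, an odds ratio of (0.50/0.50)/(0.25/0.75) = 3; 400 ATR and 1000 AF. From the subgroup section: odds ratio about 5 for age 40 or over. Assumed, because the documents give no figure: weight-bearing odds ratio 1.5–2 in half of patients; 50% to 80% aged 40 or over; two-sided alpha.

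**The plan's own figure.** n per arm = [1.96√(2×0.24×0.76) + 1.2816√(0.28×0.72 + 0.20×0.80)]²/0.08² = 597. The total is 1194, and 1194/0.9 = 1327. With continuity correction it is 622 per arm, and 1244/0.9 = 1383. Both are consistent with at least 1400.

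**Interval, no covariates.** Let b be the log odds ratio. Direct conversion is p0 − expit(logit p0 + b). With p0 held fixed, its SE is p1(1−p1)·SE(b).
- SE(b) = √[1/(630×0.2016) + 1/(630×0.16)] = 0.1334.
- Converted SE = 0.16 × 0.1334 = 2.13 points.
- Full SE = √[(0.2016 + 0.16)/630] = 2.40 points, a 95% half-width of 1.96 × 2.40 = 4.70.
- The converted SE is therefore 11% too small (2.13/2.40 = 0.89).
- When p1 = p0 the two formulas coincide, so there is no shortfall under no effect.

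In 400,000 simulated trials per setting, the converted 95% interval covered 91.9% at 8 points, 93.8% at 4 points and 95.0% at zero.

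**Point estimate.** Solve for the intercept and the treatment odds ratio that give average risks of exactly 28% and 20% over the covariate cells, then convert at 28%. With injury type:
- The model odds ratio is 0.628, against a marginal 0.643.
- Control risks are 21.3% (AF) and 44.8% (ATR); IPC risks are 14.5% and 33.7%.
- Standardised: (1000/1400)(21.3 − 14.5) + (400/1400)(44.8 − 33.7) = 8.0 points.
- Direct: odds 0.28/0.72 × 0.628 = 0.244, risk 19.6%, reduction 8.4 points.

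| Covariates in the model | Direct, true 8.0 | Direct, true 4.0 |
|---|---|---|
| Weight-bearing only (assumed OR 1.5–2) | 8.05–8.15 | 4.03–4.09 |
| Injury type | 8.38 | 4.22 |
| Injury type + age OR 5 in all (80% to 50% aged ≥40) | 8.67–9.09 | 4.38–4.63 |
| Injury type + age as main effects, age effect in ATR patients only (80% to 50%) | 8.45–8.53 | – |

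The last row matters because the age odds ratio comes from an Achilles-only trial. The plan describes adjustment for factors and adds interactions only for treatment-by-subgroup tests.

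**Direction.** With injury type and age (50% aged ≥40), a true harm of 28% vs 36% converts to 9.6 points rather than 8.0. The shift magnifies whichever effect exists.

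**Standardisation.** In simulated trials (20,000 per scenario) across these covariate sets, delta-method standardisation averaged 7.97–8.02 and 3.97–4.03 points, with 94.7–95.3% coverage.

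**The case against.** The strongest reply is that the plan does specify a method, by citation. If the cited paper standardises, neither problem arises. If it converts at mean covariates, the exaggeration is smaller: 8.17 with injury type, and 8.03–8.21 with age in all patients. This stands. The documents show an unstated method with a possible fault, not a demonstrated error.

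The larger shifts also rest on stacked assumptions. Reaching 9.1 needs injury type and age both as adjusters, an Achilles-trial age effect carried over to fracture patients (at least 1000 of 1400), and half the patients aged 40 or over. For the one covariate named, the excess is 0.15 points or less, against a half-width of 4.7. This stands too.

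The interval is not always narrower. At 8 points, mean widths for direct conversion and standardisation are 8.48 and 9.14 with injury type, but 8.65 and 8.72 with injury type and age (50%). With further strong covariates the direct interval can be the wider one. The accurate charge is under-coverage at a real effect.

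The reply does not remove the interval problem under direct conversion, which is present with no covariates at all. Nor does it remove the need for the plan to state its own calculation.

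**Conclusion.** The point holds as a cheap improvement. If the adjusted odds ratio and its limits are applied to the observed control risk, a nominal 95% interval covers about 92% at 8 points and 94% at 4 points. The estimate is inflated by about 0.05–0.15 points for weight-bearing alone and by about 0.4 if injury type is a minimization factor. It is inflated by 0.7–1.1 only on the age assumptions above. These are illustrations, not bounds: two further assumed factors with odds ratios of 3, on top of injury type and age, give about 1.6.

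A reader might infer three stronger things. The documents support none of them.
- That the plan is biased towards IPC. The shift exaggerates harm as readily as benefit and vanishes under no effect.
- That the primary conclusion is at risk. The adjusted odds ratio, its interval, its test and the sample size are untouched.
- That a decision at 4 points could be tipped. No decision rule is set there, and the plan does not say which estimate enters the economic model.

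**What to change.** Keep the logistic model and the adjusted odds ratio. Replace the conversion sentence with marginal standardisation. From the same model, predict each analysed patient's risk under IPC and under control, average each over all analysed patients, and report the risk difference and risk ratio with delta-method or bootstrap 95% intervals.

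List the minimization factors, and say whether surgery and LMWH enter the model. Standardise only over covariates fixed at or before randomization. The Intervention and Comparator paragraphs have weight-bearing set by the surgeon and recorded for the immobilization period. Weight-bearing, surgery and LMWH should therefore enter as recorded or planned at baseline. Later values should be left out of the model used for this calculation.

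The cost is a few lines of text and standard software output, with no new data. The reported reduction may be slightly smaller, and its interval usually slightly wider, than under direct conversion.

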The mean inclusion per hospital is (one)-two AF each week and one ATR every second week, which totals at least a mean of 75 patients/hospital/year⁹. With 1,5 patients included per week per each hospital (20 hospitals registered), we will finish inclusion within one year.

For the secondary patient-reported outcomes, the trial has more than 95% power (alpha 0.05) to identify a clinically relevant difference, which at one year is 10 points difference on the rating scales (0-100)²⁰. For the explanatory VTE-preventive mechanisms (blood serum test) and collagen production (microdialysis) earlier studies demonstrate that a sample size of 100 gives 90% power to detect significant differences between groups, which will save expenses.

Treatment compliance of the patients, which was 91% in our earlier study, will be registered both by the IPC-device and by the patient. Patients will daily register the number of hours that IPC was used.

Material: Patient selection – population, sample

Male and female patients aged between 18 and 75 years with an acute injury requiring lower-leg immobilization, i.e. acute unilateral ATR or isolated AF, in a hospital setting will be eligible. The exclusion criteria will be: inability to give informed consent; planned follow-up at another hospital; renal failure; heart failure with pitting oedema; thrombophlebitis; malignancy; peripheral vascular disease; haemophilia/thrombophilia and pregnancy⁹.

The randomising clinician or nurse will screen for eligible patients as soon after their presentation to hospital as possible. To minimize differences between hospitals, patients will be eligible for inclusion if treatment starts within 10 days after the injury. IPC-prophylaxis for

DVT may have greater effect if started early after injury, but these potential differences will also be considered below. The responsible clinician collects the baseline data necessary to complete a randomization form. He/she then will randomize patients via a central, web-based service (RedCap) by giving the baseline data (which are then stored securely) and receives the treatment allocation at the end of the session.

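### Score and continuous outcomes get unadjusted two-group tests with no prespecified estimate or confidence interval, although the patient-reported scores are powered on a 10-point difference

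*Combined protocol and SAP*

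**What the plan says.** The section Statistical analysis plan treats outcomes differently by type.

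- Binary outcomes: odds ratios with 95% confidence intervals, "adjusted using logistic regression for the factors used in the minimization algorithm and weight-bearing".
- Ordinal scores: "Group differences for ordinal secondary outcome data, such as the patient-reported data (ATRS and OMAS), will be analyzed by nonparametric tests". The choice is fixed in advance.
- EQ-5D-5L, FAOS and continuous outcomes: these "will be analyzed by t-tests if the data are normally distributed, and using an appropriate nonparametric test otherwise". Neither the normality criterion nor the alternative test is named.

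For the last two groups the section names no covariate, effect measure or confidence interval.

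Other sections bear on this. Estimated sample size and power claims more than 95% power for the patient-reported outcomes to find a clinically relevant difference, "which at one year is 10 points difference on the rating scales (0-100"). It gives no standard deviation. Variables and measures promises group means, medians, SDs and ranges, and places these scores at 6 and 12 months; no baseline score is described. Study Design (PICO) says in general terms: "Surgery vs. no surgery will be accounted for in the statistical analysis" (Patients), "Weight-bearing will be recorded and accounted for in the statistical analysis" (Intervention and Comparator) and "LMWH vs. no LMWH will be accounted for in the statistical analysis" (Comparator). None of these says which outcome or which model is meant.

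**The concern.** Patient-reported outcome is the named secondary outcome, and the Outcome paragraph relies on it to confirm a long-term effect on VTE and healing. Three things are missing from its analysis.

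First, the target is a difference in points, but a rank test neither tests nor estimates a difference in mean points. A non-significant rank test of ATRS or OMAS would not show whether 10 points had been excluded.

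Second, when allocation is balanced on prognostic factors and the analysis ignores them, the standard error still contains between-factor variation that the design has removed. Intervals are then too wide and the test rejects less often than 5% under the null.

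Third, for EQ-5D-5L, FAOS and continuous outcomes, the quantity being compared is unknown until the data have been inspected.

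**Working it through.** **The plan's own figure.** The power of more than 95% cannot be reproduced, because no SD is stated. It can be inverted. With two-sided alpha 0.05 (sidedness is not stated, so this is assumed), the largest SD that still gives 95% power for 10 points is 10 / [(1.960 + 1.645) × √(2/n)], with n per arm after 10% drop-out.

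- ATR: 400 × 0.9 / 2 = 180 per arm, SD up to 26.3
- AF: 1000 × 0.9 / 2 = 450 per arm, SD up to 41.6
- All: 1400 × 0.9 / 2 = 630 per arm, SD up to 49.2

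**Cost of ignoring the balancing factors.** Let R² be the share of outcome variance that the minimization factors explain. The documents give no value, so a range is shown. The interval is too wide by the factor 1/√(1 − R²). With balanced allocation, the type I error is 2 × P(Z > 1.96/√(1 − R²)).

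| Assumed R² | CI too wide by | Actual type I error |
|---|---|---|
| 5% | 2.6% | 4.4% |
| 10% | 5.4% | 3.9% |
| 20% | 12% | 2.8% |
| 30% | 20% | 1.9% |

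**Injury type alone, for an outcome pooled across ATR and AF.** The 400:1000 mix gives p(1 − p) = (400/1400) × (1000/1400) = 0.204. With an assumed within-group SD of 20 and a mean difference D between injuries, the SE ratio is √(1 + 0.204 D²/400). For D of 5, 10, 15 and 20 points it is 1.006, 1.025, 1.056 and 1.097. At D = 20 the implied R² is 81.6/481.6 = 17%, and the type I error is about 3.2%. For a score analysed within one injury group this component is zero.

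**Effect on the smallest score set (ATR, 180 per arm), for 10 points.**

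| Assumed SD | Power, unadjusted | R² = 0.1 | R² = 0.3 |
|---|---|---|---|
| 20 | 99.7% | 99.9% | 99.99% |
| 25 | 96.7% | 97.9% | 99.5% |
| 30 | 88.5% | 91.5% | 96.6% |

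At SD 25 the 95% CI half-width is 1.96 × 25 × √(2/180) = 5.2 points unadjusted, 4.9 at R² = 0.1 and 4.3 at R² = 0.3. For AF, unadjusted power is already 99.9% at SD 30.

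**The rank test and the normality check.** Under normality a rank test has relative efficiency 0.955. At SD 25 and 180 per arm, power goes from 96.7% to 96.0%. The two-stage rule (Shapiro test in both arms, then t-test or Mann-Whitney) was simulated with 3,000 runs per scenario, at 50 and 180 per arm, for a skewed and a near-normal score bounded at 0 and 100. Type I error was 0.049 to 0.051. The t-test was chosen in 0% to 0.6% of runs with the skewed score and in 79% to 92% with the near-normal one.

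**The case against.** The best defence is that any error is on the safe side and often small. An unadjusted test that is conservative cannot create a false claim of benefit, and at SD 25 or below the power loss is slight. That stands. So does the point that the R² and SD values are assumptions. The documents never list the minimization factors, and the description of randomisation mentions only a central web-based service. If allocation were in fact simple randomisation, the unadjusted type I error would be 5%. Adjustment would then still narrow the interval, but it would not correct an error.

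It can also be said that rank tests follow from classing ATRS and OMAS as ordinal, and that the general statements on surgery, weight-bearing and LMWH may be meant to cover these outcomes. The first is a coherent choice, but it does not fit a target in points. The second leaves an ambiguity: no method named for these outcomes could carry a covariate.

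Several stronger readings are tempting, and the documents do not support them:

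- That a normality check picks the test for every patient-reported score. It does not apply to ATRS or OMAS.
- That the check inflates false positives. The simulation shows no inflation; the objection is to prespecification and interpretation.
- That the 10-point difference cannot be estimated. A t-test yields a mean difference, and the promised means and SDs allow a crude one for every score. What is missing is a prespecified estimate with its interval.
- That baseline scores are being wasted. None is described, so only covariates are at issue.
- That every useful covariate is already on the randomisation form. Its items are not listed.

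**Conclusion.** The point holds as a gap in estimation and prespecification, with a modest loss of precision. As written, the plan gives score and continuous outcomes neither the adjustment nor the interval that it gives binary outcomes, and for ATRS and OMAS the planned inference is not on the scale used for power.

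The 3% to 20% excess CI width and the 4.4% to 1.9% type I error both depend on the assumed R² of 5% to 30%; the type I figures also need allocation to be balanced on those factors. The upper part of the range is hard to reach from injury type alone, even when ATR and AF are pooled (R² about 17% in the most extreme case shown). Within one injury group, and with no baseline score, the low end is more likely. The figures do not show that the patient-reported analysis is underpowered: the claimed power holds unadjusted up to an SD of 26.3 in the smallest group.

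**What to change.** In the Statistical analysis plan:

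1. List the factors used in the minimization algorithm.
2. For each score and continuous outcome, make the main analysis a linear regression on allocation plus those factors, with robust standard errors. Add injury type where ATR and AF are pooled and it is not already a factor.
3. Report the adjusted mean difference with its 95% CI. For the 0-100 scales, interpret it against 10 points; the EQ-5D index is on another scale and needs its own reference value or none.
4. Do not let a normality check choose the method. Keep the rank tests as a named sensitivity analysis.
5. State whether the general commitments on surgery, weight-bearing and LMWH extend to these outcomes, and give the SD behind the power claim.

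The cost is wording. No more patients are needed, and any factor used to allocate patients must already have been recorded. The one real downside is that a mean difference treats the ordinal ATRS and OMAS as numeric scores, but the 10-point target already does so.
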